timeline for the Baseline survey. If so, we will continue to allow them to participate in the study without complete they daily spending surveys, so long as the Baseline survey is completed prior to the first intervention session. This will enable us to still collect data about outcomes besides out-of-pocket costs of care. A follow up survey will be sent immediately after the participant completes the intervention (within 48 hours) and will also ask about participant satisfaction with CONFIDENCE. A second follow up survey will be sent 8 weeks after the intervention is complete. After the participant completes the second follow up survey, they will receive a second set of daily spending diaries administered in the same way as the first set of diaries. Follow up surveys are expected to take approximately 20 to 30 minutes to complete. Participants will receive up to 5 reminders to complete the baseline and follow up surveys, include 3 emails prompts and up to 2 phone calls. Participants will receive a text message reminder, if they choose, reminding them to complete daily spending surveys each night. **Qualitative interviews.** Up to 15 participants will also be asked to participate in a one-on-one qualitative, in-depth, semi-structured interview as well about their experiences with the program, which is expected to take approximately 45 minutes depending on how much the participant would like to share. Selection of interview participants will be based on purposeful sampling, with the goal of recruiting a qualitative sample that includes a range of care experiences according to participant gender, age, employment status, and kin relationship to the person to whom care is provided. Interviews will be completed over Zoom and recorded and later transcribed. Participants will be invited to complete this interview after completing the CONFIDENCE program. If the participant agrees to participate, they will receive a study information sheet by email prior to attending the interview and will review this information sheet before completing the interview. **Payment for surveys and qualitative interviews.** Amazon gift cards will be sent to participants by email for each study activity (surveys and interviews). We will pay participants for the baseline and first set of diaries surveys within a week of when the first set of diaries are due. A second payment will be administered within a week of the first follow up survey being completed. The remaining payments will be sent the week of the second set of diary surveys are due/completed. Payment for interviews will be sent within 1 week of completing the interview. Participants may earn up to \$125 for participating, or \$150 if they complete the qualitative interview. Participants may earn \$25 for each study activity. **Fidelity.** Fidelity will be monitored by an observer (PI or research assistant) and the CONFIDENCE program facilitators. We will monitor one randomly selected CONFIDENCE lesson for each cohort. The selected lesson will be based on Stata's random number generator. The facilitators will know in advance of each lesson if selected for monitoring so they may record lesson. The facilitator will be sent a survey within 24 hours of completing selected sessions to self-monitor delivery. Fidelity surveys will be sent by the PI using REDCap. Session recordings will be stored in the USC CONFIDENCE Office 365 Shared folder and deleted once fidelity forms are completed. The research assistant or PI will watch the recording and complete the fidelity survey within 2 weeks of the lesson taking place. **Attendance.** The USC facilitator will monitor attendance at CONFIDENCE sessions and will store this information in a shared Office 365 folder. The study team will extract information about attendance from study participants from Excel files where attendance is marked and enter it into REDCap for study participants. **Comparison of registrant demographics and study participants.** In addition to data collected from surveys, we will compare the demographic characteristics of individuals who register for CONFIDENCE to participate in the educational program alone with those of study participants. This information can help to inform future recruitment methods by helping the study team understand differences in the characteristics of those who choose to participate in research and those who do not. As a part of their funder's requirements, USC must report on demographic characteristics of program participants to the sponsor. They currently collect this information using the Eventbrite registration page. The Case Western investigators will already have access to the Eventbrite form information to identify participants who are interested in participating in the research study. To compare the characteristics of study participants to non-study participants, we will download Excel files directly from Eventbrite onto an encrypted university Box folder, and add an indicator variable to indicate whether or not individual registrants were in the research study. Once this occurs, all identifiable information will be removed from Excel files and the file will be saved so we can conduct analyses and compare characteristics of study and non-study participants. **Participant safety and monitoring adverse events.** *Adverse events.* Adverse events and protocol deviations will be recorded on an adverse event form by the study team member (PI or RA) who first observes this event. Adverse events pertaining to participant safety and confidentiality will be promptly reported by the PI by phone. Where the RA or PI suspects risk of harm to self or others, this will be reported to USC PI [name], who is a licensed clinical psychologist with extensive experience working with caregivers. [name] is the director of the USC Family Caregiver Support Program where CONFIDENCE is being administered. She will reach out to the participant by phone to conduct further assessment and a safety plan. All protocol deviations and adverse events will be promptly reported to the Institutional Review Board by the PI. Serious adverse events will be reported within 24-hours. **Data and Safety Monitoring.** The PI will complete a Data Safety Monitoring Report every 6 months of the study. The Data Safety Monitoring Report will include the following core elements: a) Progress towards enrollment and participant retention; b) Participant characteristics for enrolled and retained participants (e.g., age, race, ethnicity, gender, aspects of the caregiving situation) according to intervention status; and c) Documentation of adverse events, serious adverse events, and unanticipated problems, as defined below, including resolution of these events and study protocol modifications. This report will not contain any participant identifiers. This report will be shared with the USC PI for review.

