17.0 Data Analysis Plan

Directions: Describe the data analysis plan, including any statistical procedures. If applicable, provide a power analysis, and study/safety endpoints. Directions: Describe the data analysis plan, including any statistical procedures. If applicable, provide a power analysis, and study/safety endpoints

Participant Demographic Characteristics

Participant characteristics, including age, gender, race, ethnicity, educational attainment, income, employment status, kin relationship to recipient, length of time caregiving, hours of caregiving, and whether the care recipient and caregiver live together will be reported using frequencies, percentages, means, and standards of deviation. *Comparison of Study and non-study participants*. Demographic characteristics of study and non-study participants collected from Eventbrite will be compared using t-test and chi-squared bivariate analyses, as well as frequencies and percentages. **Outcome Measures** *Self-Efficacy (primary outcome)*. Self-efficacy is measured using the Caregiver Self-Efficacy Scale. This 8-item scale combines domains of self-efficacy (e.g., managing behavioral symptoms, accessing respite, and controlling upsetting thoughts. It demonstrates high reliability ($\alpha=0.89$) and good test-retest reliability (0.73). Participants rate the extent to which they are “Not confident at all” (1) to “Totally confident” (10). Scores range from 8 (lowest) to 80 (highest).³⁵ *Resourcefulness (primary outcome)*. Resourcefulness is measured using the 19-item learned resourcefulness scale designed for family caregivers ($\alpha=0.81$). This scale has two factors: one focused on help-seeking and another on self-help. Caregivers are asked the frequency at which they use different strategies to manage challenges, and may respond: . Items are added together to create a total score. Scores range from 0 to 24. Permission was received by the scale’s author to use this tool on April 21, 2022.

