Psychological Financial Strain (secondary outcome). Our measure for psychological financial strain is derived from multiple scales, which were selected according to relevance to our caregiving population. Items 1 to 11 ask about financial anxiety and is based on the 10-item scale from Shapiro & Burchell (2012).³⁶ Item 1 is modified such that the question asks about feeling overwhelmed instead of bored. We also added an item based on another related to caregiving (i.e., “I find planning for my caregiving expenses to be unpleasant”). Items 12 to 14 are based on those used by Novilitis et al., (2003), and address additional components of financial anxiety than those items introduced by Shapiro (e.g., arguments with others; $\alpha=0.74$).³⁷ Lastly, we included the 1-item question from Shim et al. (2010) that asks about financial worry (“I worry constantly about money”; CFA factor loading was 0.79 for this item).³⁸

Monthly Spending Report (out-of-pocket costs of caregiving, secondary outcome). Our measure for monthly out-of-pocket costs of caregiving is based on the tool used by the AARP Public Policy Institute in their 2016 report on the out-of-pocket costs of caregiving. We will calculate estimated daily costs using both period survey and daily survey. Period surveys (i.e., baseline and the second follow up surveys) ask about spending: in the last month (30 days) and in the last 12 months but not the last month. When a caregiver indicates paying for an item in the last month, they are asked to provide an estimated cost. (We do not ask about cost in the last year given the likelihood the participant will not be able to accurately recall this cost and may forget some expenses.) The costs for yearly/monthly item are those believed to occur irregularly, such as purchase of devices and rent payments. Daily costs are those anticipated to occur regularly, and are asked about on daily surveys, such as groceries and recreation items for the care recipient. To calculate monthly spending, we will multiply daily spending by 6 to approximate 30

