days in a month and add all monthly expenses. While the measure is subject to recall bias and fluctuations in spending, it balances 1) the need to efficiently collect data and 2) reduces recall bias by relying on monthly recall alone. Analysis of Baseline and Follow Up Measures We will used two sets of paired t-tests to examine changes in scores between baseline and follow up surveys. If we discover a p-value of <0.05 after running tests, this will indicate there was a statistically significant difference between scores. We will compare scores from baseline until the first follow up survey and from baseline until the second follow up survey. In addition, we will examine mean scores at each time point, as well as the standard of deviation for all summed scores on each scaled. **Handling of Missing Data Missing daily surveys.** If participants miss a survey, we will adjust the monthly formula such that we will multiply according to the number of days for which surveys are completed to reach 30. For example, if a participant completed 4/5 surveys, we will multiply by 7.5 instead of 6. We will exclude participants who miss more than 2 daily surveys from analyses when examining monthly costs. **Missing data on follow up surveys.** Although data from all participants will be reported in sample descriptives, for all analyses using t-tests, we will use a complete case analysis such that participants with any missing data will be removed from the analytic sample. Although this approach risks missing data bias, multiple imputation and maximum likelihood estimation are not feasible to conduct with bivariate analyses. We will conduct bivariate analyses using a "dummy" variable to identify potential differences between those with complete and incomplete data and will also report the extent of missingness using frequencies and percentages.

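### The plan rejects imputation and likelihood methods on a mistaken ground; add a mixed model beside the complete-case paired t-tests, and state exclusions by outcome, follow-up and item.

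*Combined protocol and SAP*

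**What the plan says.** Section 17.0 compares each outcome before and after the programme by paired t-test: "We will compare scores from baseline until the first follow up survey and from baseline until the second follow up survey". For all of these tests, "we will use a complete case analysis such that participants with any missing data will be removed from the analytic sample". The plan acknowledges that this may bias the results, then gives its reason: "multiple imputation and maximum likelihood estimation are not feasible to conduct with bivariate analyses". It will report how much is missing and compare people with complete and incomplete data. No other inferential efficacy analysis is described.

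Monthly spending has its own diary rule: one or two missed diaries are rescaled, and beyond that "We will exclude participants who miss more than 2 daily surveys from analyses when examining monthly costs". Spending is asked at two visits only: "Period surveys (i.e., baseline and the second follow up surveys) ask about spending". Section 12.0 keeps people who have no baseline diaries, on the ground that "This will enable us to still collect data about outcomes besides out-of-pocket costs of care".

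The self-efficacy scale has 8 items and the resourcefulness scale 19. Section 17.0 gives no rule for scoring a scale with a skipped item. Section 23.0 allows a participant to be removed when a survey is largely blank (its example is more than half missing), but that is a removal rule and not a scoring rule.

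**The concern.** The stated reason is technically wrong. A paired t-test estimates one mean change. That change can be calculated in each imputed data set and pooled, or read as a visit contrast from a likelihood-based model of the three visits.

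As written, someone who answers follow-up 1 but not follow-up 2 contributes nothing to the follow-up 2 estimate, although two of their scores are in hand. The baseline scores of leavers are not used either. With a single arm, the pre-post change is the only efficacy evidence, so if staying is related to the scores the estimate shifts and no control group absorbs the shift. The completer comparison, the survey reminders (12.0) and the completeness check (28.0) describe or limit the loss. None of them alters the estimate.

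Two wording gaps go with this. The exclusion clause does not say that it works outcome by outcome and follow-up by follow-up. Taken as it stands, it also drops a pair when a single item is skipped.

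**Working it through.** **The plan's own figure.** For 60 complete pairs, two-sided alpha 0.05 and 80% power, the noncentral t gives a detectable change of 0.368 SD of change. This fits the plan's description of a small to moderate effect. With visit correlation r = 0.6, the SD of change is √(2(1 − 0.6)) = 0.894 score SD, so the detectable change is 0.368 × 0.894 = 0.329 score SD.

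**Feasibility.** On a simulated complete data set of 60, an unstructured REML model gave visit contrasts of 0.06999 (SE 0.1009) and 0.09506 (SE 0.12659). These equal the paired t-test results, with 59 degrees of freedom.

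**Inputs for bias (assumed unless noted).** n = 60; 25% loss; no true change; scores with SD 1 and equal correlation r between visits. I used r = 0.6 and r = 0.73, the latter being the test-retest figure that section 17.0 gives for self-efficacy. The odds of staying rise 1.65-fold per SD of whatever drives loss (log-odds 0.5). Stayers then average about δ = 0.12 SD above the whole sample on that driver. Write s = √(2(1 − r)), which is 0.894 or 0.735.

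**Expected bias in score SDs.**

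| Loss depends on | Visit | Complete case | Likelihood |
|---|---|---|---|
| Low baseline stays | either | (1 − r)δ = 0.048 / 0.032 | 0 |
| Follow-up 1 change; only follow-up 2 missed | 2 | δs/2 = 0.054 / 0.044 | 0 |
| Follow-up 1 change; both missed | 1 | δs = 0.107 / 0.088 | δs(1 + r)/2 = 0.086 / 0.076 |
| Same | 2 | δs/2 = 0.054 / 0.044 | rδs/2 = 0.032 / 0.032 |
| Follow-up 1 score; both missed | 1 | (1 − r)δ = 0.048 / 0.032 | (1 − r²)δ = 0.077 / 0.056 |
| Same | 2 | 0 | r(1 − r)δ = 0.029 / 0.024 |
| Follow-up 1 score; only follow-up 2 missed | 2 | 0 | 0 |
| Random | either | 0 | 0 |

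Paired entries are r = 0.6 / r = 0.73. Simulation (20,000 to 40,000 trials per case) agrees with every row to within about 0.002. If the driver works the other way, for example if improvers leave, the signs reverse.

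**Reading the table.**
- When change-driven leavers miss both surveys, the model removes a share (1 − r)/2 of the follow-up 1 bias (20% at r = 0.6, 14% at r = 0.73) and 1 − r of the follow-up 2 bias (40%, 27%).
- When the follow-up 1 score drives loss and both surveys are missed, the complete-case change partly cancels the selection, because stayers' own baselines are raised too. The model adjusts for baseline only by the slope r and keeps more of the bias.
- False positives at a nominal 5% (r = 0.6, change-driven loss): with only follow-up 2 missed, 6.9% complete case against 4.9% likelihood; with both missed, 12.7% against 10.2% at follow-up 1.
- For scale, 0.054 / 0.329 is about one sixth of the detectable change.
- Under random loss the follow-up 2 SE is 0.133 complete case and 0.129 likelihood, a difference of 3%.

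**Skipped items.** With an assumed independent skip rate q per item and k items in each of two surveys, pairs kept = 60(1 − q)^(2k). At q = 0.5%: 60 × 0.995^16 = 55.4 for self-efficacy and 60 × 0.995^38 = 49.6 for resourcefulness. At q = 1%: 51.1 and 41.0. If the skips are strongly clustered in a few people, the loss is smaller (56.5 and 53.8 kept at 0.5%).

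**The case against.** The strongest reply is that the model is not reliably less biased. The gains come from mechanisms in which the observed scores explain the loss. Caregivers who finish with low confidence and then stop responding are just as plausible, and for them the table shows complete case doing better. The documents give no loss mechanism, so this stands. A reader might infer that a likelihood model should replace the t-tests because it corrects the bias; the documents do not support that.

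A reader might also infer that the mistaken sentence is why t-tests were chosen. The plan names the t-tests first and uses the sentence later to defend complete-case handling, so deleting it alone would change no result.

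A third tempting reading is that the exclusion clause removes anyone missing anything, including people without diaries, from every test. The clause sits under missing follow-up survey data, diaries have their own rule, and section 12.0 keeps people without diaries for the other outcomes. Exclusion by outcome and by follow-up is the likely intent, so this is a matter of wording. Removing a pair for one skipped item is likewise a rule, if a strict one. The survey instruments are separate attachments, so item skipping may already be limited in ways not visible here.

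Finally, this is a pilot that admits the bias risk and reports missingness. That lowers the priority. It does not make the stated reason correct.

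**Conclusion.** The feasibility statement is wrong, and the plan leaves collected scores unused. That much needs no assumption. The practical size is modest and conditional: about 0.03 to 0.05 SD of avoidable bias in the favourable mechanisms, partial correction if change-driven leavers return neither survey, and a worse answer from the model if loss then follows the follow-up 1 score. Random loss causes no bias, and complete case gives up only about 3% in SE relative to the model.

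These figures rest on the assumed 25% loss, the strength of selection and equal visit correlations. Monthly spending was not simulated. The supportable conclusion is that a second analysis belongs beside the t-tests, not that the t-tests are invalid. The scope and item-scoring points are clarifications. Overall this is a minor to low-priority fix, with high confidence in the wording points and less in the size of any benefit.

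**What to change.** 1. Delete the sentence saying that imputation and likelihood methods cannot be used.
2. For self-efficacy, resourcefulness and financial strain, add a linear mixed model with visit as a factor, unstructured covariance, REML and small-sample degrees of freedom. Include all eligible, non-fraudulent participants with at least one score. Report both visit contrasts next to the paired t-tests.
3. For monthly spending, use a two-visit version that also keeps people with only one usable visit, such as those without baseline diaries.
4. Call a change robust only if the two analyses agree. State that the model assumes missing at random and can be more biased than complete case when leavers return no follow-up. Report the number of such losses and the reasons, including removals after a care recipient's death (23.0).
5. Say that t-test exclusion applies separately to each outcome and each follow-up, in line with section 12.0 and the diary rule.
6. Replace exclusion for one skipped item with each instrument's own scoring rule, or a prespecified proration threshold where it has none. Say how this fits the removal rule in section 23.0.

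The cost is a revised paragraph and a few lines of standard code, with no new data or participants. The downside is a little more analysis and reliance on an assumption that the data cannot test.

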18.0 Confidentiality of Data

1. To maintain the confidentiality of the data:

- I will use a unique study identifier to code individuals' identifiable data and will store the master list separate from the study data.
- I will use a unique study identifier to code individuals' data, but it will never be linked to a master list.
- Other- please explain: [Click here to enter text.](#)

Provide a plan to maintain or destroy identifiers once analysis of identifiable information is complete. All study identifiers will be removed from REDCap survey files and we will also delete the study key once findings are published. Session recordings will be deleted once fidelity monitoring is complete for that session.

- I attest that any recordings (audio or video) saved to a portable device will be deleted by formatting the device's storage memory.

How are you storing your electronic data?

- CWRU Redcap
- CWRU Secure Research Environment (SRE)
- CWRU Box
- OnCore
- CWRU Secure Network Drive
- Zoom Cloud
- Portable device (must be encrypted, not just password protected)
- Other - List storage method and provide justification: Data about participant attendance and session recordings used for fidelity monitoring will be temporarily stored in an Office 365 Folder shared by partners at USC, wherein folders must be shared by USC for others to access contents.

Please note: if you're storing or entering your electronic data in any system other than an approved system listed above, please contact the CWRU IRB ([contact]).

2. I acknowledge that paper research data and documents will be stored in a double-locked secure environment in the following **location**: [Click here to enter text.](#)
 - We will not have paper research documents.
3. Will data be shared?
 - Yes
 - List the exact data elements that will be shared: De-identified survey data from the baseline, follow up, and diaries surveys will be shared, as well as de-identified qualitative interview transcripts with USC

- Describe how data will be sent: De-identified data will be shared by email

No

N/A

If sharing data, please complete a request to ensure the proper contracts/agreements are in place: <https://case.edu/research/faculty-staff/technology-transfer/material-transfer-data-use-agreements>

